RESEARCH PROTOCOL

Reducing Diagnostic Error to Improve Patient Safety in COPD and Asthma (REDEFINE Study)

Version: 1.5

Date: 1/11/2018

Principal Investigator: [name] MD MPH

Division of Pulmonary, Critical Care, Sleep, and Allergy, Department of Medicine, University of Illinois at Chicago, Chicago, IL

Sponsor: AHRQ 1R01HS024964-01

SPECIFIC AIMS AND HYPOTHESIS

Aim 1: Determine the prevalence of and characteristics associated with diagnostic error (DE) in asthma and/or COPD in an underserved population

Aim 2: Evaluate the effectiveness of the REDEFINE program compared to usual care on health care utilization and patient-centered outcomes (including respiratory medication use, all-cause emergency room visits, and all-cause hospitalizations)

Hypothesis:

The REDEFINE program will reduce health care utilization and improve patient-centered outcomes compared to usual care.

Aim 3: Evaluate the cost impact and cost effectiveness of the REDEFINE program versus usual care

Hypothesis:

The REDEFINE program will be cost-effective in the management of patients with COPD and asthma compared to usual care.

BACKGROUND AND SIGNIFICANCE

Asthma and chronic obstructive pulmonary disease (COPD) are common chronic lung diseases that are diagnosed in more than 30 million adults in the United States.^{1,2} However, diagnostic error (DE), considered one of the most common and harmful of patient-safety problems by the Institute of Medicine,^{3,4} occur frequently with asthma and/or COPD and disproportionately affect minorities and the underserved. DE leads to lost opportunities to identify other chronic conditions, avoidable morbidity and mortality, unnecessary costs to patients and health systems, and poor quality of care.³⁻⁶ Shortness of breath or dyspnea, which is a common symptom in asthma and COPD, is also common for many other chronic conditions such as cardiovascular disease and obesity. A better understanding of the impact of DE and interventions to improve diagnostic accuracy in asthma and COPD are of particular importance for minorities and the underserved that are disproportionately affected by conditions leading to dyspnea.

Spirometry is a simple, mobile, and essential test that is recommended by all major national and international guidelines for the diagnosis of asthma and COPD.⁷⁻¹⁰

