2. If the spirometry findings are normal, with approval from the PCP, will de-escalate respiratory medication therapy via a stepwise process and schedule patient back for a repeat pre and post bronchodilator spirometry within 1-2 weeks at the same time and place as the PCP clinic session. Again with the PCP approval, this deescalation and repeat spirometry can occur in 1-2 week intervals until all maintenance medications are discontinued as long as the pre and post spirometry continues to be normal. After each visit, the following will be provided to the provider and patient: a letter summarizing the interpretation of the findings using GOLD/GINA criteria with recommendations for initial guideline driven therapy based on GOLD/GINA guidelines, if appropriate. Subjects will be managed by their PCP thereafter.
3. All spirometry test results and the subject's assessment at the time of the test will be uploaded into the subject's electronic health record for future reference.

D) Outcome Measures:

1. Primary outcome:

- (i) Accurate classification of patient as having COPD and/or asthma
- (ii) All-cause and respiratory related, acute care outpatient visits, ED visits, and hospitalizations

2. Secondary outcome:

- (i) Appropriate use of respiratory medications based on guidelines
- (ii) Use of other diagnostic testing: ECG, echocardiograms, CT/CXR, stress testing, cardiac catheterization, other pulmonary function tests
- (iii) Initiation of guideline based therapy
- (iv) Quality of life measures

E) Data collection and follow-up

1) Baseline data collection obtained at visit zero (V_0), in addition to those listed under intervention and usual care:

- 1. Demographic data (gender, age, self-reported race)
- 2. SES related measures: median household income
- 3. Level of education
- 4. Type of health insurance or self-pay
- 5. Up to two emergency contacts information
- 6. List of current respiratory medications from subject's pharmacy and verification with patient
- 7. Co-morbidities
- 8. History of prior ED visits or hospitalizations in the past one year with associated cause
- 9. EQ-5D 5L +B Bolt-on
- 10. SF-36 short form
- 11. Social support survey

2) All subjects will have their medical charts reviewed every 3 months after the initial visit (MR_1 , MR_2 , MR_3 , MR_4) up to one year. These electronic medical chart reviews will be used to obtain follow-up data since last study contact.

- 1. Change in type of health insurance or self-pay

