- 2. List of current respiratory medications from subject's pharmacy and verification with patient
- 3. Use of diagnostic testing: ECG, echocardiograms, CT/CXR, stress testing, cardiac catheterization, other pulmonary function tests
- 4. Any ED visits or hospitalizations or acute outpatient care visit and associated cause.
- 5. Healthcare utilization outside of U of I system (e.g. testing such as spirometry, ED and hospitalizations) if available through scanned records

3) All subjects will be contacted every 3 months after the initial visit via telephone (T_1 , T_2 , T_3 , T_4) up to one year; or they will be given the option to complete in person based on subject's convenience, for example they have a doctor appointment near time of study follow-up. These phone calls will be used to obtain follow-up data since last study contact. A reminder post-card will be mailed to the subjects a month before the next telephone contact.

- 1. Change in type of health insurance or self-pay

2. List of current respiratory medications from subject's pharmacy and verification with patient
3. Use of diagnostic testing: ECG, echocardiograms, CT/CXR, stress testing, cardiac catheterization, other pulmonary function tests
4. Any ED visits or hospitalizations or acute outpatient care visit and associated cause.
5. Healthcare utilization outside of U of I system (e.g. testing such as ancillary testing, ED and hospitalizations)
6. mMRC
7. A respiratory exacerbation history
8. EQ-5D 5L +B Bolt-on
9. SF-36 short form (at 3, 6 and 12 months)
10. Social support survey (at 6 months and 12 months)

F) Monetary compensation of subjects

1. PCP compensation:

UI Health and MSHC PCPs will receive \$95 in cash after completion of the education session. For CCHHS PCPs, the Division or Department will receive a total of \$95 per participant to be part of the divisional fund to be used by the PCP at their discretion as allowed by their institution.

2. Patient subject compensation:

Baseline visit (Vo):

Same for Intervention and usual care groups: Subjects will be provided \$75 in cash for completing the initial study visit.

Telephone contact (T₁-T₃):

Same for Intervention and usual care groups. Subjects who choose to complete the follow-up in person or via telephone will receive \$20 in cash at the time of the visit or at a later specified time that is convenient for the subject.

Final contact (T₄):

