5. STATISTICAL ANALYSES

All data will be stored in a secure, locked location. Data will be entered and managed through the Research Electronic Data Capture (REDCap). REDCap is a secure web-based application for building and managing online databases. REDCap is provided by

the CCTS Design Analysis Core. Data will be analyzed for clinical effectiveness using intention-to-treat principles.⁶⁹⁻⁷¹ For **Aim 1**, we will evaluate the misdiagnosis rates of the intervened and usual care groups separately at the first visit. Then compare rates between groups by using a generalized linear mixed model for binary outcome with two cluster levels, PCP and hospital, to account for the dependence within clusters. For the **Aim 2**, to investigate the impact of the misdiagnosis over time (4 time points: 0, 3, 6, 9, 12 months) on the quality of life and healthcare utilization, we will fit generalized linear mixed models with time, group, and their interaction as the main predictors. Two cluster levels, PCP and hospital, will be specified in the model to account for the dependence within clusters^{72,73} and an appropriate link function will be used for each outcome. Clinical important confounders will also be adjusted in the models. Before these analyses we will use descriptive statistics to describe the sample, and any assumption behind each statistical method will be examined during the analysis. A two-sided p-value less than 0.05 would be considered as statistical significance. All the analyses will be conducted by using SAS 9.2 (SAS Inst., Cary, NC).

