For **Aim 3: Costs**: The intervention costs for the study include the cost of the spirometry test, the time of the CHW/health promoter, and time of pulmonologist to provide periodic oversight of spirometry validity. In addition to estimating the costs associated with the intervention it will be important to measure the healthcare utilization for participants included in the study. It is possible that the intervention leads to use of other healthcare resources, particularly if the patient is determined to be free of respiratory disease. Therefore, we will measure both respiratory-related and overall healthcare costs. To measure these costs, we will determine overall healthcare utilization and apply unit costs to each of the events. Using chart reviews, we will examine healthcare utilization during the follow-up period. We will categorize healthcare utilization into either respiratory-related or all other healthcare use. We will apply standardized prices to each of the utilization components to estimate the overall and respiratory-related healthcare resource use during the study period. The standardize prices will be based on either the National Committee for Quality Assurance standardize price list for their relative resource use measure or Medicare reimbursement rates. For medications, we will rely on average wholesale price of medications to assign an average price to each of the COPD and asthma-related medications.

Cost-Effectiveness: The secondary outcome measures included in the study will be used to estimate the effectiveness to be used in the cost-utility analysis. We will use responses to the EQ5D to estimate patient utility and use that in calculation of quality-adjusted life-years (QALY). The area under the curve will be compared between the two groups and the difference will be the incremental effect used in the cost-utility analysis.

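### Two to six unranked primary utilization outcomes share one unadjusted two-sided 0.05 threshold, with no rule for which result supports reduced utilization

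*Combined protocol and SAP*

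**What the plan says.** Section 4.D gives the second primary outcome as one line: "All-cause and respiratory related, acute care outpatient visits, ED visits, and hospitalizations". The first primary outcome, classification of the patient, belongs to Aim 1 and is a separate question.

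The claim to be tested is the Aim 2 hypothesis: "The REDEFINE program will reduce health care utilization and improve patient-centered outcomes compared to usual care".

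Section 5 says of Aim 2 that "we will fit generalized linear mixed models with time, group, and their interaction as the main predictors" and that "an appropriate link function will be used for each outcome". The only decision threshold is general: "A two-sided p-value less than 0.05 would be considered as statistical significance".

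The documents contain no ranking of the utilization outcomes, no composite, no multiplicity adjustment, no choice between the group effect and the group-by-time interaction as the deciding test, and no statement of how many or which results must be significant for the hypothesis to count as supported.

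**The concern.** Two cause categories crossed with three visit types give up to six primary utilization outcomes. With one unadjusted threshold and no decision rule, nothing fixed in advance separates a planned success from the most favourable of several results. The more outcomes that may carry the claim, the larger the chance that at least one is significant when the program does nothing. At stake is whether a reported reduction in utilization can be read as confirmation of the Aim 2 hypothesis at the stated 5% level. The open choice of model term adds a further degree of freedom, since each outcome can be judged on the group effect or on the interaction.

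**Working it through.** The plan states no familywise error rate and no power, so there is no figure to reproduce.

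**Inputs from the documents**
- Outcomes: {all-cause, respiratory-related} × {acute outpatient, ED, hospitalization} = 2 × 3 = 6 if each is tested separately (section 4.D). Read as one all-cause and one respiratory composite, the line gives 2. Counting only the two all-cause outcomes that Aim 2 names also gives 2.
- Threshold: two-sided 0.05 for each test (section 5).

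**Assumptions, because the documents give no values**
- One signed, one-degree-of-freedom test per outcome.
- Correlation between visit types, r: 0.1 to 0.9.
- Share of all-cause variance carried by respiratory events, s: 0.1 to 0.9.

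**Step 1: independence, as a ceiling for comparison.** Chance of at least one significant result among k tests:
- k = 6, either direction: 1 − 0.95^6 = 26.5%; in the program's favour: 1 − 0.975^6 = 14.1%.
- k = 2: 1 − 0.95^2 = 9.75%; in favour: 1 − 0.975^2 = 4.9%.

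**Step 2: allow for overlap.** Respiratory events are a subset of all-cause events, so the tests are positively correlated. For each visit type take z_all = √s · z_resp + √(1 − s) · z_nonresp, with correlation r between visit types, and simulate under no effect (1,000,000 draws per combination of r and s).

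| Reading | In the program's favour | Either direction |
|---|---|---|
| Six outcomes, r = 0.1, s = 0.1 | 13.3% | 25.7% |
| Six outcomes, r = 0.5, s = 0.5 | 10.1% | 20.2% |
| Six outcomes, r = 0.9, s = 0.9 | 5.3% | 10.7% |
| Two composites, whole range | 3.2-4.8% | 6.5-9.5% |
| Two all-cause outcomes, whole range | 3.5-4.9% | 7.0-9.8% |
| One test | 2.5% | 5.0% |

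**Step 3: what the signed test assumes.** If the interaction decides and time is treated as categorical, the test has several degrees of freedom and no single favourable direction. Only the either-direction column is then relevant.

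**Step 4: the two candidate rules.**
- Holm across six holds the familywise two-sided error at 5% or less by construction. Its strictest step is 0.05/6 = 0.00833, critical z = 2.638.
- Power there, for an outcome with an assumed 80% at 0.05: Φ(1.960 + 0.842 − 2.638) = Φ(0.164) = 56.5%. With an assumed 90%: Φ(1.960 + 1.282 − 2.638) = Φ(0.604) = 72.7%.
- Under a strict fixed order any rejection needs the first test to succeed, so the error with no effect on any outcome is 2.5% in favour and 5% in either direction.

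**The case against.** Three points on the other side have force.

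First, six is a reading. The outcome is a single run-on line, and the phrase about a link function for each outcome follows a sentence that names only quality of life and utilization; it may refer to those two domains. Section 5 never lists six models. A reader might infer that the plan commits to six separate tests; the text does not establish that. This lowers the size of the problem without removing it, since two outcomes already exceed the single-test level.

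Second, the plan nowhere says that one significant result is enough. A reader might infer an any-one-wins rule, but the documents are silent on the rule altogether. In a comparative effectiveness trial, reporting related facets of utilization side by side with estimates and intervals is defensible. It does not, however, tell the reader what would confirm a directional hypothesis attached to outcomes labelled primary.

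Third, a reader might infer that Aim 2 contradicts section 4.D because it names "including respiratory medication use, all-cause emergency room visits, and all-cause hospitalizations" and leaves out acute outpatient and respiratory-related visits. The word that opens that parenthesis makes the list illustrative. It is neither a rival list of endpoints nor a ranking, so it does not conflict with section 4.D and does not supply the missing order.

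**Conclusion.** The concern holds as a missing decision rule. The plan labels two to six utilization outcomes as primary, tests at an unadjusted two-sided 0.05, and does not say which outcome or model term decides. With no program effect, the chance of at least one significant favourable result is about 5-13% (11-26% in either direction) on the six-outcome reading and about 3-5% (6.5-10%) on a two-outcome reading, against 2.5% (5%).

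Confidence is high for the omission, and for the error exceeding the single-test level on every reading examined. It is lower for the exact size, which depends on the count of outcomes and on correlations and respiratory shares that the documents do not give. The favourable-direction figures further require a signed one-degree-of-freedom test. A narrower range such as 10-13% would need the six-outcome reading together with low to moderate correlations and respiratory shares, and the documents support none of these. The data remain usable; the change should be made, but the trial's design does not depend on it.

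**What to change.** In section 5, before outcome data are analysed:

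1. State how the section 4.D line is to be counted, and name the one model term (the group effect, or group by time) that is the deciding test for each utilization outcome.
2. Adopt one of two rules.
   - (a) Holm's procedure across the listed utilization outcomes at familywise two-sided 0.05.
   - (b) A strict fixed order with a single first outcome chosen by the sponsor: for example one of the two all-cause outcomes named in Aim 2, then the other, then the rest, each tested at 0.05 only if all earlier ones succeed. The first place must hold one outcome. Putting two there in parallel, each at 0.05, restores the two-outcome error.
3. State that classification (Aim 1) does not count as evidence of reduced utilization.

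This is wording only and needs no new data. The cost of (a) is power: with six outcomes, an assumed 80% (90%) falls to about 56% (73%) at the strictest step; with two, where that step is 0.025, it falls to about 71% (84%). The cost of (b) is that later outcomes cannot be claimed once an earlier one fails; the first loses nothing. The documents give no event rates, so the actual power loss cannot be sized.

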4. DESCRIPTION OF PROCEDURES

A) PCP Education and Randomization:

After obtaining PCP informed consent and prior to patient recruitment, a one hour educational session will be held for PCPs participating in the study. The purpose of this session is to provide education to PCPs about COPD, asthma, spirometry, and GOLD and GINA guidelines (GOLD=Global Initiative for Chronic Obstructive Lung Disease, GINA=Global Initiative for Asthma). The educational session will provide continuing medical education credit to those who attend. The learning objectives will be the following: 1) Review COPD and asthma disease definition, presentation, diagnosis and testing including spirometry, 2) be familiar with the GOLD and GINA guidelines and recommendations for therapy.

PCPs who consented to participate in the study and completed the education session will be randomized to have their patients who meet the study criteria receive the intervention or usual care.

B) Patient subject- Intervention:

On the day of the outpatient visit, subjects will be advised to arrive 90 minutes prior to their clinic visit in the same building as the clinic site or the CRC (Clinical Research Center at UIC). The following information will be collected and procedures will be performed:

1. Subject demographic and contact information
2. Co-morbid conditions
3. Smoking history
4. Medication history from patient and also from pharmacy used by subjects
5. A respiratory exacerbation history in the past year
6. Modified Medical Research Counsel (mMRC) dyspnea scale and COPD Assessment Test
7. Quality of life measures
8. Pre and post-bronchodilator (BD) spirometry
9. De-Escalation Spirometry Screener for patients de-escalating based on spirometry (See Based on spirometry findings)
10. De-Escalation Phone Script

Based on spirometry findings:

1. If the spirometry findings are consistent with COPD and/or asthma, the following will be provided to the provider and patient to have available during the clinic visit: a letter summarizing the interpretation of the findings using GOLD/GINA criteria with recommendations for initial guideline driven therapy based on GOLD/GINA guidelines. Subjects will be managed by their PCP thereafter.

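### The Aim 2 model lists month 0 for healthcare utilization, but acute outpatient visits have no baseline count, and ED visits and hospitalizations are counted over 12 months at baseline against about 3 at each follow-up

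*Combined protocol and SAP*

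**What the plan says.** Section 4.D defines primary outcome (ii) as "All-cause and respiratory related, acute care outpatient visits, ED visits, and hospitalizations".

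Section 4.E.1 is introduced as "Baseline data collection obtained at visit zero (V_0), in addition to those listed under intervention and usual care", so it must be read together with the visit lists for the two arms in 4.B and 4.C. Its only utilization item is number 8: "History of prior ED visits or hospitalizations in the past one year with associated cause". The nearest item in the arm-specific lists is "A respiratory exacerbation history in the past year", which appears in both.

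For follow-up, section 4.E.2 states "All subjects will have their medical charts reviewed every 3 months after the initial visit", and "These electronic medical chart reviews will be used to obtain follow-up data since last study contact". Both the chart-review list and the telephone list (4.E.3) then collect "Any ED visits or hospitalizations or acute outpatient care visit and associated cause".

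Section 5, Aim 2, describes the time axis of the model as "4 time points: 0, 3, 6, 9, 12 months) on the quality of life and healthcare utilization". The model has terms for time, arm and their interaction, and the link is to be chosen for each outcome. The sentence announces four time points and lists five. It mentions no offset, no conversion to rates and no separate treatment of month 0.

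**The concern.** The model calls for a month-0 value of utilization that the data collection does not supply in usable form. One primary component has no value there. The other two have a value on a different exposure base.

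Two things are at stake. First, the fitted time course of utilization will show a steep fall after enrolment that reflects only the shorter counting window. Second, under some analyses that the plan's wording permits, the mismatch also leaks into the group-by-time interaction, the term most likely to be read as the treatment effect. In addition, acute outpatient visits cannot be adjusted for their own baseline level, in a trial that randomizes at most about 80 PCPs, where chance imbalance between arms is plausible.

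**Working it through.** The plan states no event rate, effect size or power for utilization, so there is no figure of its own to reproduce. The check compares the item lists and then works out what the unequal windows do.

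**1. Item lists**

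| Component of primary outcome (ii) | Baseline | Each follow-up |
|---|---|---|
| ED visits | past 12 months | since last contact, about 3 months |
| Hospitalizations | past 12 months | since last contact, about 3 months |
| Acute outpatient visits | not listed | since last contact, about 3 months |

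The past-year respiratory exacerbation history could capture some respiratory visits but not an all-cause count.

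**2. Effect on the time course**

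Let λ be the annual rate (assumed 0.5, 1 or 2, constant, no treatment effect) and w the window in years (1 at month 0, 0.25 afterwards). The expected count is λw, and P(any event) = 1 − exp(−λw).

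| λ | Count, month 0 | Count, quarter | P(any), month 0 | P(any), quarter |
|---|---|---|---|---|
| 0.5 | 0.50 | 0.125 | 0.39 | 0.12 |
| 1 | 1.00 | 0.25 | 0.63 | 0.22 |
| 2 | 2.00 | 0.50 | 0.86 | 0.39 |

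The count ratio is 0.25/1 = 0.25 whatever the rate: a 75% fall in both arms with nothing changing. An offset of log(w) restores the ratio to 1.00.

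**3. Effect on the group-by-time contrast**

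This depends on the link and the time coding. Assumed scenarios are a persistent 1.2 to 1.0 rate imbalance with no treatment effect, or a true follow-up rate ratio of 0.8 with arms equal at baseline.

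- *Log link, categorical time.* At each time point log(λ₁w) − log(λ₀w) = log(λ₁/λ₀), so w cancels. A true 0.8 is recovered as 0.80 with or without the offset.
- *Log link, linear time, constant rate ratio.* The arms' expected counts are proportional at all five times, so the slopes are equal and the interaction ratio is 1.00.
- *Log link, linear time, ratio changing from 1.0 to 0.8.* Poisson models fitted to the expected counts (no random effects) give a 12-month interaction ratio of 0.70 without the offset and 0.77 with it. The gap between 0.77 and 0.80 comes from fitting a straight line to a step. The move from 0.77 to 0.70 comes from the window mismatch. The usual-care 0-to-12-month ratio is 0.20 without the offset and 1.00 with it.
- *Identity link, persistent imbalance, no effect.* The interaction is (1.2λ − λ)(0.25 − 1) = −0.15λ, that is −0.075, −0.15 and −0.30 visits per window at λ = 0.5, 1 and 2. The true value is 0.
- *Any-event logit, persistent imbalance, no effect.* The odds are exp(λw) − 1. At λ = 1 the odds ratio is (e^1.2 − 1)/(e^1 − 1) = 1.35 at month 0 and (e^0.30 − 1)/(e^0.25 − 1) = 1.23 per quarter, so the interaction is 1.23/1.35 = 0.91. At λ = 0.5 and 2 it is 0.96 and 0.81. With matched windows it is 1.00.

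**The case against.** The strongest reply is that utilization outcomes are counts, that the natural link for counts is the log, and that section 5 promises a suitable link and a check of assumptions. Under a log link with categorical time the interaction is untouched by window length. A persistent imbalance does no harm under linear time either. The distorted results need a binary or identity-link analysis that the plan does not name, or linear time with a changing rate ratio. This stands, and it limits what can be claimed about bias. It does not settle the matter, because the plan fixes neither link nor time coding, and no link can supply a missing outpatient count.

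A second reply is that month 0 may be meant only for quality of life, which is measured at the baseline visit, with the announced four time points being the four quarterly reviews of utilization. That is a plausible reading. But the sentence gives one list of five times for both outcomes, so the reader cannot tell.

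Third, past-year ED visits and hospitalizations can serve as covariates under the planned confounder adjustment, and earlier outpatient visits may be retrievable from charts. Both are true and make the repair easy. However, the protocol's outcome chart reviews start only after the initial visit, and no look-back for outpatient visits is planned.

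**Conclusion.** The point holds as a mismatch between the data collected and the model. As written, the Aim 2 model cannot be fitted at month 0 for acute outpatient visits. For ED visits and hospitalizations it would show a false 75% fall in counts in both arms. The 75% follows from the 12-month and nominal 3-month windows and a constant rate.

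Distortion of the group-by-time contrast is conditional. It is absent under a log link with categorical time, and under a log link with linear time when the arms' rate ratio is constant from baseline. It is present under an any-event logit (0.96 to 0.81), an identity link (−0.075 to −0.30 visits per window), and a log link with linear time when the ratio changes (0.70 against 0.77). The event rates, the 20% imbalance and the 0.8 effect are assumptions, since the documents give none of them.

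A reader might infer that the treatment comparison is therefore biased, or that it cannot be made without a month-0 value. The documents do not support either. They do not commit to an analysis in which the bias arises, and randomized arms can be compared on post-baseline counts alone. For acute outpatient visits the loss is mainly precision and adjustment for chance imbalance. The gap should be closed before analysis, but it does not invalidate the trial.

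**What to change.** In section 5, state that utilization at month 0 is not an outcome. Model the four quarterly counts (MR1 to MR4) with a log link and log person-time as offset, which also handles intervals that are not exactly 3 months. Adjust each component for its own prior-year count. Keep month 0 as a time point for quality of life, and correct the number of time points for each outcome.

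In section 4.E.1, extend item 8 to acute outpatient visits in the 12 months before the baseline visit, taken from the EMR in both arms with the definitions used at MR1 to MR4.

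Other repairs would deal with the ED and hospitalization windows, such as a 3-month look-back at baseline or an offset with month 0 retained. Neither supplies the outpatient count.

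The cost is a small amount of extra abstraction plus the change of wording. Section 3 already has charts reviewed at prescreening and one EMR system at all sites, so the item could be collected retrospectively for patients already enrolled, as far as their charts hold it. The gain is precision, adjustment for chance imbalance among at most about 80 PCPs, and a model that the collected data can support.
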